### **7.3.4. Pooling of Investigational Sites**

The data from all study centers will be pooled together for all planned analyses.

### **7.3.5. Coding Conventions for Events and Medications**

All adverse events, and medical history will be mapped to the Medical Dictionary for Regulatory Activities (MedDRA Version 24.1) system for reporting (preferred term and body system).

Prior and Concomitant medications will be coded using WHO-DD (Drug Dictionary) (Version date September 2021 B2/B3).

### **7.3.6. Analysis Software**

Data manipulation, tabulation of descriptive statistics, calculation of inferential statistics, and graphical representations will be performed primarily using SAS (release 9.4 or higher) for Windows. If the use of other software is warranted, the final clinical study report will detail what software was used and for what purposes.

### **7.3.7. Study Data**

Study data identified in the schedule for time and events (Table 1) are collected, and source verified, on the electronic data capture (EDC) tool: Laboratory data are not collected in the EDC tool and are provided from external laboratories.

All study data will be formulated into regulatory compliant data sets to provide transparency, traceability, and integrity of trial analysis results from the collection source.

## **7.4. Planned Study Analyses**

### **7.4.1. Statistical Summaries: Descriptive and Inferential**

All statistical tests will be two-sided and a difference resulting in a p-value of less than or equal to 0.05 will be considered statistically significant. All p-values will be rounded to and displayed in four decimals. If a p-value less than 0.0001 occurs it will be shown in tables as <0.0001.

Descriptive summaries of variables will be provided where appropriate. For continuous variables, the number of non-missing values (n) mean, standard deviation, median, minimum, and maximum will be tabulated by treatment. For categorical variables, the counts and percentage of each value will be tabulated by treatment. Expansion of descriptive table categories within each treatment may occur if such elaborations are thought to be useful.

All study related data collected will be presented in listings. Study related data not subject to analysis according to this plan will not appear in any tables or graphs but will be included in the data listings.

### **7.4.2. Interim Analyses**

No formal interim analysis is planned for this study.

### **7.4.3. Final Analysis and Publication of Study Results**

The final analysis will be completed after all subjects have completed Visit 6 or prematurely discontinued the study.

## **7.5. Multiple Testing Procedures**

The primary efficacy analysis will be the between-group comparison of the mean IOP values in the study eye at each time point at each of the Visit 4/Day 15, Visit 5/Day 42, and Visit 6/Day 84 visits (i.e., a total of 9 between-group comparisons). A hierarchical analysis will be conducted to compare each of the investigational products against the comparator, timolol 0.5%, as follows: (1) BTQ-1902, (2) BTQ-1901B, and (3) BTQ-1901A.

To demonstrate noninferiority, the upper limits of the 2-sided 95% confidence interval (CI) for the difference between each comparison should be lower than 1.5 mm Hg at all timepoints. Additionally, the upper limits of the 95% CI should be lower than 1.0 mm Hg for the majority of time points measured (i.e., 5 of 9).

All other comparisons are considered exploratory.

## **8. SUMMARY OF STUDY DATA**

### **8.1. Subject Disposition**

A summary of the analysis sets includes the number and percentage of subjects for the following categories: subjects screened, subjects screen failed, subjects randomized, subjects in ITT Population, subjects in Safety Population, subjects in the PP Population, and subjects in the PK Population. All percentages will be based on the number of subjects randomized.

End of trial information will also be summarized in this table, including the number of subjects completing the study/treatment and the number of subjects that prematurely discontinued the study/treatment with reasons for withdrawal. All percentages will be based on the number of subjects randomized.

A by-subject data listing of study completion information including the reason for premature study withdrawal and also treatment completion status, if applicable, will be presented.

### **8.2. Protocol Deviations**

Major protocol deviations, as determined by a Sponsor masked review of the data prior to database lock and unmasking of the study, may result in the removal of a subject's data from the PP Population. The Sponsor or designee will be responsible for producing the final deviation file; this file will include a description of the protocol deviation and clearly identify whether or not this deviation warrants exclusion from the PP Population. This file will be finalized prior to database lock.

All protocol deviations will be presented in a data listing, with a flag to indicate if a deviation was considered major and resulted in the exclusion of the subject from the PP Population. A summary table will be generated based on the classification of protocol deviations.

### **8.3. Demographics and Baseline Characteristics**

Subject demographic data and baseline characteristics will be tabulated and summarized descriptively by treatment group and overall. The demographic data and baseline characteristics will be summarized for all analysis populations (ITT, SAF, PP, and PK). Individual subject demographics and baseline characteristics will be provided in listings.

The demographics consist of age (year), sex, race, ethnicity, and iris color. The baseline characteristics consist of baseline diagnosis of Primary Open-Angle Glaucoma and Ocular Hypertension by eye (right eye [OD] and left eye [OS]), designated study eye (OD, OS), baseline systolic/diastolic BP (mm Hg), baseline HR (beats/min), baseline Visual Field testing results (mean deviation), baseline LogMAR BCVA, and pachymetry.

Age, baseline systolic/diastolic blood pressure, baseline heart rate will be summarized using descriptive statistics. The number and percentage of subjects by sex, race, ethnicity, and iris

color will also be reported. Percentages will be based on the total number of subjects in the study population presentation.

All demographic and baseline information will be listed by subject.

#### **8.4. Concurrent Illness and Medical Conditions**

The number and percent of subjects with medical/ophthalmic histories will be summarized for all subjects by the type of history and eye (ophthalmic history: study eye, ophthalmic history: non-study eye, non-ocular medical history) and treatment group. Individual subject listings will also be provided for concurrent illness and medical history.

Medical history will be coded using the MedDRA Version 24.1. The number and percentage of subjects with any medical history will be summarized overall and for each system organ class (SOC) and preferred term (PT). Percentages will be calculated based on number of subjects in the Safety Population.

Subject medical history data including gonioscopy will be presented in a listing.

#### **8.5. Prior and Concomitant Medications**

The number and percentages of all ocular concomitant medications will be summarized by study/non-study eye and treatment group, Anatomical Therapeutic Chemical (ATC) level 2, and PT. The total number of concomitant medications and the number and percentages of subjects with at least 1 concomitant medication will be summarized by treatment group. All summaries will be performed using the Safety Population.

A concomitant medication is defined as any medication taken on or after the day of first exposure to study drug up until 7 days after last dose of study drug.

Prior medications are defined as any medications started and stopped prior to the day of first exposure to any study drug.

Non-ocular medications will be summarized similarly.

#### **8.6. Treatment Compliance**

Continuous descriptive summaries will be presented for the Safety Population by treatment level and will include number of doses, number of doses missed, and study dosing compliance (%). Compliance is calculated for each subject using the following formula:

$$\frac{((\text{Date of last dose} - \text{Date of first dose} + 1) \times 2 \text{ doses} - \text{Missed doses})}{((\text{Date of last visit [Visit 6 or ET]} - \text{Date of Visit 3} + 1) \times 2 \text{ doses})} \times 100\%$$

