7.3. Criteria for Withdrawal from the Study/Criteria for Discontinuation of Study Medication

The following are the criteria for considering withdrawal from the study:

- Withdrawal of subject consent. The subject may request for any reason at any time to be withdrawn from the study.
- Subject lost to follow-up.
- The Sponsor terminates the study (see Section 6.4).

If a subject withdraws from the study, the principal reason for withdrawal will be recorded in the electronic case report form (eCRF). Subjects who are withdrawn will not be replaced.

If a study subject fails to attend a study visit at any point during the study period, every effort should be made to keep the subject in the study and conduct all study visits as scheduled; all attempts to contact the subject must be documented. If the subject relocates during the study period, the clinical research organization (CRO), should be contacted to determine if there is a possibility that the subject could continue at another clinical site.

The following are criteria for considering discontinuation from study medication:

- Pregnancy: If a subject becomes pregnant during the study, the subject will be withdrawn from study medication and followed through the conclusion of the pregnancy (Section 9.5.3).
- Adverse event: A clinically significant or serious AE (SAE) that in the Investigator's or Medical Monitor's judgment, suggests that continued administration of study medication is not in the subject's best interests for safety reasons. Additionally, if an AE requires treatment, the Investigator in consultation with the Medical Monitor may determine that study medication should not be concurrently administered with a required concomitant medication.
- Intraocular pressure in either eye >34 mm Hg during the treatment period.
- Subject request: Subject requests to be withdrawn from study medication.

When possible, a decision to discontinue a subject from study medication should first be discussed with the Medical Monitor. If a subject is discontinued from study medication, every effort should be made to encourage the subject to continue to attend study visits to be followed for safety, rather than withdrawing the subject from the study or, failing that, to perform all early discontinuation assessment procedures at the visit the subject is withdrawn (Section 10.5).

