8.4. Treatment Compliance

Treatment compliance will be monitored by subject-reported missed doses assessed at each treatment visit (Visit 4/Day 15, Visit 5/Day 42, and Visit 6/Day 84) via response to the Missed Doses Log. Subjects will be asked to log if they have missed any doses since the previous visit, and if so, the date of missed dose, which dose was missed (AM and/or PM), which eye was not dosed (right, left, both), and the reason for the missed dose. These data will be analyzed to determine an estimate of compliance over the duration of the study.

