8.5.3. Study Medication Accountability

An unmasked staff member *not* involved in performing endpoint procedures will maintain full accountability records for the study medication and will be responsible for recording the receipt, dispensing, and return of all supplies of the study medication using the inventories supplied by the Sponsor. At each visit subsequent to Visit 3/Qualification/Baseline (i.e., Visit 4/Day 15, Visit 5/Day 42, and Visit 6/Day 84) all bottles that were dispensed at the previous visit (empty, used, or unused) should be returned to the site in the kit. At Visits 4 and 5, study medication accountability procedures will be conducted, and new study medication kits will be dispensed for the next study period. At Visit 6 all study medication materials will be returned to the study site, and final study medication accountability will be conducted. Visit 6 will be the last day of study treatment; no further study medication will be dispensed at this visit. The monitor will review dispensing and study medication accountability records at the completion of the study and note any discrepancies. All investigational study medication must be stored in a secure facility with limited access.

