10.3. Qualification Visit

One qualification visit will be conducted, Visit 3/Qualification/Baseline/Day 1.

At Visit 3, subjects must have unmedicated IOP measurements in at least one eye ≥ 22 and ≤ 34 mm Hg at 8:00 AM and ≥ 18 and ≤ 34 mm Hg at 10:00 AM and 4:00 PM (each timepoint is ± 30 minutes). The IOP must be at least 22 mm Hg at each consecutive measurement at the 8:00 AM time point.

10.3.1. Visit 3/Qualification/Baseline/Day 1

This visit will be scheduled so that IOP can be taken at 8:00 AM, 10:00 AM, and 4:00 PM (\pm 30 minutes). If the subject has not discontinued using their prior ocular hypotensive medications for the required washout period duration (28 days for prostaglandin analogs, ROCK inhibitors or β -blockers, 14 days for adrenergic agonists, and 5 days for muscarinic agonists or CAIs), the visit will need to be rescheduled.

Procedures performed at Visit 3 include the following:

8 AM (± 30 minutes):

- AE assessment
- Concomitant medication review
- Urine pregnancy test (females of childbearing potential only); must be performed prior to randomization
- BCVA
- Grading conjunctival hyperemia (grading of conjunctival hyperemia must be performed prior to randomization)
- Biomicroscopy/
- IOP

10 AM (± 30 minutes):

- AE assessment
- HR/BP
- Biomicroscopy
- IOP

4 PM (± 30 minutes):

- AE assessment
- Biomicroscopy

- IOP
- Review eligibility criteria
- Randomize eligible subjects
- Dispense study medication
- Provide instruction and supervise guided practice of drop instillation by subject/caretaker (no evening dose should be administered at home after this visit)
- Conduct drop comfort rating following instillation of study medication (≥ 10 minutes after the IOP measurement)
- Study medication accountability (i.e., document that Kit 1 was dispensed)

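### The SAP 8.6 compliance formula counts one dose too many on Day 1 and on Visit 6, and scores the same dosing differently depending on whether a subject who stops drug stays in follow-up

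*SAP*

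**What the plan says.** SAP 8.6 introduces a per-subject ratio with the words "Compliance is calculated for each subject using the following formula". The numerator is the inclusive number of days from first dose to "Date of last dose", times 2, less missed doses. The denominator is the inclusive number of days from Visit 3 to "Date of last visit [Visit 6 or ET", times 2. Neither part is adjusted for the first or last day. The Safety Population table "will include number of doses, number of doses missed, and study dosing compliance"; the SAP gives a derivation only for the last of these three.

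The protocol fixes the dosing at each end of the treatment period:

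- **Day 1.** The initial dose is instilled at the site at the end of Visit 3, after the 4 PM pressure reading (Protocol 8.2 and 10.3.1), and "no evening dose should be administered at home after this visit".
- **Visit 6.** The morning dose is taken at the site (Protocol 8.5.2 and 10.4.3) and all remaining drug is handed back. Protocol 8.5.3 adds: "Visit 6 will be the last day of study treatment; no further study medication will be dispensed at this visit".

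Protocol 7.3 separates stopping drug from leaving the study. For a subject who stops drug, "every effort should be made to encourage the subject to continue to attend study visits to be followed for safety"; failing that, early discontinuation procedures are done. Protocol 8.4 has subjects log each missed dose, including "which eye was not dosed (right, left, both" eyes.

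**The concern.** There are two separate problems. The factor of 2 is wrong on the first and last treatment days, so the formula counts doses that the protocol does not schedule. The two parts of the ratio also stop at different dates. For a subject who stops drug early, the denominator depends on how long that subject keeps coming to visits, and that is not a matter of dosing.

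The summary would be read to judge whether the four arms were dosed comparably. If subjects who stop drug tended to stay in one arm and to leave in another, the arms could show different compliance with identical dosing. The formula also does not say whether a dose missed in one eye counts as missed.

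**Working it through.** The documents state no compliance figure, so there is none to reproduce. The SAP formula is evaluated directly below, counting Day 1 as day 1.

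**Inputs from the documents:** two doses a day (Protocol 8.5.2); one dose on Day 1 and one at Visit 6 (above); Visit 6 on Day 84 ± 3.

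**Inputs assumed:** the day drug stops, the day of the ET visit, and the number of missed doses. The documents give none of these, so ranges are shown.

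**1. Dose count for a completer.** The formula credits 2 × days; the possible number is 2 × days − 2.

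- Day 81: 162 against 160
- Day 84: 168 against 166
- Day 87: 174 against 172

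**2. Effect on a Day 84 completer's percentage.** With m missed doses the SAP gives (168 − m)/168 and the corrected ratio is (166 − m)/166. The difference is m × (1/166 − 1/168), or about 0.0072 percentage points per missed dose.

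- m = 0: 100% both ways
- m = 10: 94.05% against 93.98% (0.07 points)
- m = 20: 88.10% against 87.95% (0.14 points)
- m = 34: 79.76% against 79.52% (0.24 points)

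**3. Same dosing, different attendance.** Take the last dose on Day 42 and no missed doses, so the numerator is 42 × 2 = 84.

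- Stays to Visit 6 on Day 84: 84/168 = 50.0% (48.3% with Visit 6 on Day 87, 51.9% on Day 81)
- ET on Day 42: 84/84 = 100%
- ET on Day 43: 84/86 = 97.7%
- ET on Day 49: 84/98 = 85.7%
- ET on Day 56: 84/112 = 75.0%

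Other stopping days, with no missed doses:

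| Last dose | Stays to Day 84 | ET next day | ET 14 days later |
|---|---|---|---|
| Day 15 | 17.9% | 93.8% | 51.7% |
| Day 28 | 33.3% | 96.6% | 66.7% |
| Day 56 | 66.7% | 98.2% | 80.0% |
| Day 70 | 83.3% | 98.6% | 83.3% |

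**4. Do corrected day counts close the gap?** No. A last dose on the evening of Day 42 is 2 × 42 − 1 = 83 doses. Staying to Day 84 gives 83/166 = 50.0%. ET on Day 43 gives 83/84 = 98.8% or 83/85 = 97.6%, depending on whether one or two doses are scheduled that day. The gap comes from the denominator's end date.

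**5. Does a common end date close it?** Yes, under either definition. Adherence while on drug gives 83/83 = 100% for both subjects. Share of the planned course gives 83/166 = 50.0% for both.

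**The case against.** The strongest reply is that 50% is a legitimate answer. Protocol 8.4 describes compliance over the duration of the study, and a subject followed to Day 84 who dosed to Day 42 took about half of the planned course. On that view, ending the denominator at drug discontinuation is a different definition, not a correction. This stands as a point about choice of definition. It does not rescue the formula, because a subject with the same dosing who leaves the next day scores 97.7%. Under either definition one of the two is scored wrongly.

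A second reply concerns ET. Protocol 10.5 asks for the Visit 6 procedures when drug is stopped. If that visit is the ET of the formula, the gap shrinks or disappears. However, neither abbreviation list defines ET, SAP 7.3.3 ties early termination to leaving the study, and Protocol 7.3 places the early discontinuation procedures second to continued attendance. The literal end date for a subject who stays is therefore Visit 6. The ambiguity still needs to be settled.

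Several stronger readings are tempting and are not supported:

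- A reader might infer that the dose-count table is wrong for nearly every subject, by up to 480 doses (2 × 240). The SAP does not say that this count is taken from the numerator, and 480 also needs all 240 subjects to complete on drug.
- A reader might infer that subjects who stop and stay are charged for doses they were told not to take. Protocol 7.3 also lists stopping at the subject's own request.
- A reader might infer that only study-eye misses should count, because efficacy uses that eye. Both eyes are treated and the table is on the Safety Population, so that rule would be a preference.

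**Conclusion.** The formula is wrong as written in two respects, and the point is minor. The day-count error is certain from the text: 168 doses against 166 possible for a Day 84 completer. It moves a completer's percentage by no more than about a quarter of a point with up to 34 missed doses, and it overstates the reported dose count by 2 only if that count comes from the numerator.

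The mismatched end dates matter more for any subject who stops drug early. The size is illustrative: 50.0% against 97.7% rests on an assumed last dose on Day 42, no missed doses, and ET on Day 43. It is not a general property of the formula. With ET on Day 56 the second figure falls to 75.0%.

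A reader might go on to infer that this weakens the noninferiority conclusion. The documents do not support that. Compliance is only described, no test or margin uses it, and no compliance threshold defines the per-protocol population, whose exclusions come from masked review of deviations (SAP 8.2). Nor do the documents give any sign that retention after stopping drug would differ by arm.

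**What to change.** Rewrite the formula in SAP 8.6 as (scheduled doses taken) / (scheduled doses), with these rules:

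- **First and last days.** Count one scheduled dose on Day 1. On the end date count only the doses scheduled: one at Visit 6, and one if drug stops after a morning dose. Scheduled doses are then 2 × (end date − Visit 3 date + 1) − 1, less one more when only the morning dose belongs to the end date. If the time of day of a stopper's last dose is not recorded, state a convention; for a Day 42 stop against the full course it moves the result between 82/166 = 49.4% and 83/166 = 50.0%.
- **End date.** Use one rule for all subjects whatever their attendance. Either end at permanent discontinuation of drug or Visit 6, which measures adherence while on drug and needs treatment duration reported beside it, or use the planned course for everyone. Name the definition chosen.
- **ET.** Define it, and say which date applies to a subject who has discontinuation procedures and then keeps attending.
- **Eye.** State how a one-eye miss counts, for example by reporting compliance for the study eye and for either eye.
- **Number of doses.** State its derivation, using the same first- and last-day rule.

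The cost is one SAP formula and its program. The missed-dose log already records date, morning or evening dose, and eye, so no new data collection is needed.

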## 9. EFFICACY ANALYSES

Unless otherwise noted, all efficacy analyses will be completed using PP and ITT Populations. All efficacy analyses will be completed using the planned dose that the subject was randomized to.

Efficacy data will be presented in tables of descriptive statistics and frequency distribution. All summary tables will be supported with individual subject data listings.

In general, and unless otherwise noted, data summaries will be presented by treatment.

### 9.1. Primary Efficacy Analysis

The primary efficacy analysis will be the between-group comparison of the mean IOP values in the study eye at each time point at each of the Visit 4/Day 15, Visit 5/Day 42, and Visit 6/Day 84 visits (i.e., a total of 9 between-group comparisons).

A summary of the efficacy endpoints will be prepared at each time point.

The between-treatment comparison will employ a mixed model for repeated measures (MMRM) with treatment, visit/time, treatment-by-visit/time interaction, and average baseline value as fixed effects, and actual IOP value in the study eye as the outcome variable of the model. Visit/time will include the following 9 timepoints: Visit 4/Day 15 (8:00 AM, 10:00 AM, 4:00 PM), Visit 5/Day 42 (8:00 AM, 10:00 AM, 4:00 PM), and Visit 6/Day 84 (8:00 AM, 10:00 AM, 4:00 PM). Average baseline value is the average result of IOP assessments performed at Visit 3/Day 1 (8:00 AM, 10:00 AM, and 4:00 PM).

An unstructured correlation matrix will be used thus allowing adjustment for correlations between time points within patients. A Kenward-Roger approximation will be used for the denominator degrees of freedom. If the model with the unstructured correlation matrix fails to converge then the following correlation structures will be fitted: variance components, compound symmetry, first order autoregressive and Toeplitz. The value of the Akaike Information Criteria (AIC) should be considered to choose the most appropriate model (the model with the smallest AIC is preferred). In case of inadequate results, further modification of the model may be required.

Example SAS code is provided below.

```
proc mixed data=eff method=reml;
  class trt visittime subjid;
  model actual=trt visittime trt*visittime avgbase/ddfm=kr;
  repeated visittime/type=UN subject=subjid;
  lsmeans trt*visittime/cl pdiff;
  run;
```

Where actual is the actual IOP value measured at each visit/time point, trt is treatment (BTQ-1901-A, BTQ-1901-B, BTQ-1902, or Timolol 0.5% ophthalmic solution), visittime is the combination of visit/timepoint (9 total values), and avgbase is the average baseline value.

Treatment comparisons will be performed for the treatment difference in least squares means (LS mean) compared with the Timolol 0.5% treatment group. LS mean (standard error [SE]) by treatment group, visit and time, the LS mean difference between treatment groups, along with 2-sided 95% CI of the treatment differences and the p-value for the treatment comparison will be displayed. To demonstrate noninferiority, the upper limits of 95% CI for the difference between each comparison should be lower than 1.5 mm Hg at all timepoints. Additionally, the upper limits of the 95% CI should be lower than 1.0 mm Hg for the majority of time points measured (i.e., 5 of 9).

Linear contrasts will be used to calculate the confidence intervals at all visit/times.

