11.3.1.2. Per-Protocol (PP) Population

The PP population consists of those subjects in the ITT population who were randomized and dosed and had no major protocol deviations. The primary efficacy analysis will be conducted on the PP population.

11.3.2. **Safety Population**

The safety population is defined as all randomized subjects who received at least one dose of the allocated study medication. All safety analyses will be performed using the safety population.

Demographics and Baseline Characteristics 11.4.

Subject demographic and baseline characteristics will be summarized for all analysis populations. Summary tables will be supported with individual subject data listings.

Efficacy Analysis 11.5.

Efficacy analyses will be performed on the PP population for the primary efficacy endpoint using observed data only. Analysis of the efficacy endpoints will also be conducted with the ITT population.

Efficacy data will be presented in tables of descriptive statistics and frequency distribution. All summary tables will be supported with individual subject data listings.

The efficacy measures (IOP) taken at Visit 3/Day 1 at 8:00 AM, 10:00 AM, and 4:00 PM will serve as baseline.

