11.5.3. Primary Efficacy Analysis

A summary of the efficacy endpoints will be prepared at each time point.

The between-treatment comparison will employ an MMRM with treatment, visit/time, treatment-by-visit/time interaction, and baseline values as fixed effects. Linear contrasts will be used to calculate the confidence intervals at all visit/times.

Sensitivity analyses include repeating the primary analysis with the ITT population, imputing missing data using multiple imputation techniques and repeating the primary analysis; utilizing LOCF imputed data and ANCOVA models at each visit/time point; and using Wilcoxon rank sum tests to compare treatments at each time point. Full details will be provided in the SAP.

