#### **3.3. Summary of Statistical Analysis Changes to the Protocol**

The analyses described in this analysis plan are consistent with the analyses described in the study protocol.

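### The primary model adjusts all nine IOP comparisons for one averaged baseline with a single slope; adding the same-clock-time baseline could narrow the noninferiority limits by up to about 7-8%, or by nothing

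*SAP*

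**What the plan says.** Protocol 11.5 names the three Visit 3 readings as the baseline: "The efficacy measures (IOP) taken at Visit 3/Day 1 at 8:00 AM, 10:00 AM, and 4:00 PM will serve as baseline". Protocol 11.5.3 lists the fixed effects of the primary MMRM, ending with "treatment-by-visit/time interaction, and baseline values as fixed effects". It does not say whether these are averaged, matched by clock time or entered together, and it leaves full details to the SAP.

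SAP 9.1 makes the choice, with "average baseline value as fixed effects, and actual IOP value in the study eye as the outcome variable of the model". The covariate is the mean of the 8:00 AM, 10:00 AM and 4:00 PM readings at Visit 3, and the example code is "model actual=trt visittime trt*visittime avgbase/ddfm=kr". There is no product of avgbase with visittime, so the slope is common to all nine visit/times. On covariance the SAP says: "An unstructured correlation matrix will be used thus allowing adjustment for correlations between time points within patients".

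Same-clock-time baselines appear elsewhere only in secondary endpoint #2 (SAP 9.2). There they form the outcome (change from the matched reading), and the covariate is again the average.

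The decision rule is in SAP 7.5: "the upper limits of the 2-sided 95% confidence interval (CI) for the difference between each comparison should be lower than 1.5 mm Hg at all" nine visit/times, and below 1.0 mm Hg at five of the nine. The products are tested in a fixed order that starts with BTQ-1902.

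**The concern.** The outcome at each visit/time is raw IOP at one clock time. If a subject's pressure tends to be high in the morning, or in the afternoon, on every day, the Visit 3 reading at that clock time predicts the later reading better than the average does. The SAP model gives that reading no weight beyond its one-third share of the mean. The common slope also prevents the baseline relation from weakening between Day 15 and Day 84 or from differing by clock time.

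The design gives some reason to expect differences by clock time. Eligibility requires at least 22 mm Hg at 8:00 AM, on each consecutive measurement, but only 18 mm Hg at 10:00 AM and 4:00 PM. When both eyes qualify, the study eye is the one with the higher 8:00 AM reading. The 8:00 AM baseline is therefore more heavily selected than the other two.

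The stake is residual variance. Nine upper limits must clear 1.5 mm Hg and five must clear 1.0, so even a modest excess in width lowers the chance that an equivalent product passes. A failure at the first step also closes the later formal comparisons.

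**Working it through.** The plan states no SD, correlation, interval width or power (SAP 6 says there was no formal calculation), so there is no figure to reproduce. The check compares models under stated assumptions.

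**From the documents:** 60 per arm, four arms, 2-sided 95% intervals, margins of 1.5 and 1.0 mm Hg, three Visit 3 readings.

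**Assumed:** complete data; equal baseline SDs; post-baseline SD 3.0 mm Hg; correlation between any two baseline readings rBB = 0.7; correlation of a post-baseline reading with its matched baseline r = 0.6, and with each unmatched baseline r − g. The gap g measures how stable clock-time patterns are.

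**Formulas** (per visit/time, as fractions of the post-baseline variance):
- Variance of the average baseline, relative to one reading: (1 + 2 × 0.7)/3 = 0.8.
- Explained by the average: A = [(r + 2(r − g))/3]² / 0.8.
- Further explained by the own-time baseline's deviation from the average: D = 2g² / [3(1 − rBB)] = 2.222 g².
- Half-width = t × sqrt(2 × residual variance / 60), with t = 1.970 on about 235 df.
- Residual variance: 9(1 − A) for the SAP model; 9(1 − A − D)(1 + 2/235) for average plus own-time baseline; 9(1 − A − D)(1 + 3/235) for all three baselines. The last factors charge for the slopes fitted at each time point.

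**Example, g = 0.2:** A = (1.4/3)²/0.8 = 0.2722 and D = 0.0889. SAP: 1.970 × sqrt(2 × 9 × 0.7278/60) = 0.921. Average plus own-time: 1.970 × sqrt(2 × 9 × 0.6389 × 1.0085/60) = 0.866.

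| Gap g | A | D | SAP half-width | Average + own-time | All three |
|---|---|---|---|---|---|
| 0 | 0.450 | 0 | 0.800 | 0.804 (+0.4%) | 0.805 (+0.6%) |
| 0.05 | 0.401 | 0.006 | 0.835 | 0.835 (0%) | 0.836 (+0.2%) |
| 0.10 | 0.356 | 0.022 | 0.866 | 0.855 (−1.3%) | 0.857 (−1.1%) |
| 0.20 | 0.272 | 0.089 | 0.921 | 0.866 (−5.9%) | 0.868 (−5.7%) |

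At SD 3.5 every width scales by 3.5/3.0 and the percentages are unchanged.

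**As a variance component.** With a persistent pattern, the subject-by-clock-time variance is g × baseline SD × post-baseline SD. With both SDs at 3.0, gaps of 0.05, 0.10 and 0.20 are 0.45, 0.9 and 1.8 mm Hg². Break-even for average plus own-time is about 0.4 mm Hg². Over a wider set of assumed variances, the SE changes by about +0.4% at variance nil, −0.5 to −3% at 0.5-1, and −5 to −8% at 2. With unequal baseline SDs, the three-baseline model reaches about −7% (0.932 to 0.868).

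**Freeing the slope alone.** There is no gain if slopes are equal. The half-width falls by up to 2.5% (0.957 to 0.933 at Day 84) if the matched correlation falls from 0.65 to 0.45 over the visits.

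**Chance of meeting the whole rule** at zero true difference (simulated, r = 0.6, rBB = 0.7), SAP model against all three baselines:
- SD 3.0: 0.69 to 0.67 at g = 0; 0.59 to 0.61 at 0.1; 0.52 to 0.61 at 0.2.
- SD 3.5: 0.45 to 0.45 at g = 0; 0.38 to 0.41 at 0.1; 0.34 to 0.44 at 0.2.

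Across the assumption sets with clock-time variance 2, the rise for the richer model is about 9-13 points.

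**Replacing the average is a different matter.** With the matched baseline alone, the half-width is 0.863 at every g: 8% wider than the SAP model at g = 0 and 6% narrower at g = 0.2. Averaging three readings removes measurement noise, so the average should stay in the model.

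**The case against.** The strongest case against is that this is a choice between valid covariate sets. The SAP's covariate is prespecified with code, and randomization protects the comparison from bias. The gain depends on a clock-time variance that neither document gives, and below about 0.4 mm Hg² the richer model loses slightly. The plan also covers part of the ground: the LOCF sensitivity ANCOVA is fitted separately at each visit/time, so it need not share a slope, and secondary endpoint #2 uses matched baselines in its outcome. All of this stands. It makes the gain conditional and the priority low. It does not remove the point, because neither of those analyses decides noninferiority.

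A reader might infer two stronger things.

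- *That the SAP changed the protocol's analysis without saying so.* SAP 3.3 states: "The analyses described in this analysis plan are consistent with the analyses described in the study protocol". The documents do not contradict this. The protocol's covariate wording is open, the average uses all three readings named as baseline, and the protocol defers detail to the SAP.
- *That Phase 3 would be planned on an inflated SD.* This does not follow. The residual SD under any covariate set can be re-estimated from the same data.

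**Conclusion.** The point holds as a conditional, low-to-modest-priority matter of precision. The SAP model is sound, and nothing here concerns bias or type I error. The limits may be up to about 7-8% wider than necessary if same-clock-time readings are clearly more strongly related than readings at different times. With weak patterns the difference is nil, or a loss of 0.4% (average plus own-time) to 0.6% (three baselines). It would be wrong to say that the limits *are* wider, because the documents contain nothing that fixes the correlation pattern. The case for acting is the asymmetry: a loss of at most about 0.6% in SE, against a possible gain of roughly 9-13 points in the chance of meeting the rule. These figures rest on assumed SDs and correlations, complete data and 60 per arm. A smaller per-protocol set would widen all the models alike.

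**What to change.** Before unmasking, change the model statement in SAP 9.1 to:

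`model actual = trt visittime trt*visittime avgbase*visittime basetm*visittime / ddfm=kr;`

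Here basetm is the Visit 3 IOP in the study eye at the same clock time (the 10:00 AM reading for the 2-hour post-dose point). Entering the three baseline readings, each crossed with visittime, is an acceptable alternative. Keep the average in the first version; do not swap it for the matched reading. Use the same covariates in the ITT, LOCF/ANCOVA and multiple-imputation repeats.

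One practical detail: center basetm at its clock-time mean. Otherwise the displayed LS means are evaluated at a baseline pooled over clock times. The treatment differences and their limits are the same either way.

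Cost: one line of text and code, and no new data, since eligibility already requires all three readings. The slopes rise from 1 to 18 (17 more), or to 27 (26 more) with three baselines. That is one or two extra per time point, at a cost of at most about 0.6% in SE. If the sponsor prefers to keep the current primary model, the same specification could be added as a prespecified sensitivity analysis, but it would then not affect the noninferiority decision.
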